8.2.2. Interim Analysis

No interim analysis is planned.

8.2.3. Handling of Missing Data

No missing data imputation is planned. For subjects with missing data, outcomes may be interpolated or last observation carry forward methods may be applied in the exploratory analysis.

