Summary of Study Procedures: Clinical Site Procedures: Two parallel subject segments will be enrolled, including (1) mTBI patients with recent injury in Segment 1 and (2) subjects without recent TBI injury of similar age and demographic characteristics (non-TBI controls in Segment 2). Baseline health information, demographics, and medical history (including prior TBI injury) will be collected for both segments. Subjects will attend up to four sequential visits relative to injury date (mTBI subjects) or first study scan date (controls): Visit 1 = ≤ 72 hr, Visit 2 = 7 ± 2 days, Visit 3 = 14 ± 2 days, and Visit 4 = 90 ± 7 days. The mTBI subjects (Segment 1) may start at Visit 1 or Visit 2. Each visit will include a clinical neuropsychological assessment battery and MR scan with GE Research Pack II (including research sequences and clinically useful T1, T2, Flair, and reconstructed SWI and DTI) will be evaluated by the site. Laboratory Procedures: Clinically acquired MR data (DICOM, P-files, and auxiliary files) will be transferred to an imaging laboratory for GE Research Pack II reconstruction of clinically useful views using multiband technology and study post-processing. Post-processed data and evaluations (as indicated on a per-module basis by the Sponsor) will be collected.	

FOOTNOTES CORRESPONDING TO NUMERALS IN THE TEXT

¹ The University of Michigan Site (originally Site 007) is removed due to non-participation.

Number of Subjects: Data will be collected for two groups (segments) of subjects: (1) mTBI subjects in Segment 1; and (2) non-mTBI controls in Segment 2. The target of the study is to collect at least 210 complete datasets from mTBI patients and at least 105 complete datasets from control subjects. Accounting for all possible reasons, attrition is estimated at 40%. Thus, a maximum of 350 mTBI subjects and 175 non-TBI controls may be enrolled across all sites. While it is expected that sites should enroll approximately equal numbers of subjects, if possible, all sites are encouraged to accrue eligible mTBI subjects as rapidly as possible on an ongoing basis until the maximum number of subjects across all sites is reached. Thus, it is prospectively expected that per-site accrual may vary based on actual enrollment rates.

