Additionally, up to 10 volunteers without mTBI injury and not requiring urgent medical care (Segment 0 volunteer subjects) may be enrolled per-site for training and retraining purposes on study devices.

Each site should enroll approximately half as many control subjects as mTBI subjects that complete two consecutive visits and thus provide two consecutive data points (complete either Visits 1 and 2, or Visit 2 and 3), e.g., one control may be enrolled for every two mTBI subjects. A report of mTBI subject enrollment will be generated by the Sponsor or its delegated contract research organization (CRO) and provided to the site on a monthly basis (30±7 days). The report will categorically detail the number of mTBI subjects completing at least 2 visits based on (in order of priority) gender, age, handedness, highest educational level, and MR system used (if more than one system used at the site) as detailed in [Section 5.1.1. Enrollment of non-mTBI controls](#).

Controls are required to attend Visits 1 and 4, but may also attend Visit 2 and 3 when available. Per site, controls should be enrolled in a manner that achieves the same overall ratio within each characteristic category as the mTBI population that has completed two visits to date (per site, all mTBI patients enrolled from study start to date of monthly summary analysis), with the priority detailed in Table 2 of this protocol.

Device/Product GEHC Modality: Magnetic Resonance (MR)

Device/Product Description:

The device under study is the *GE Research Pack II* advanced MRI application suite developed by the Sponsor, GE Healthcare (GEHC), which consists of acquisition software executable on commercially available Discovery MR750 3.0T/Discovery MR750w 3.0T MR scanners and software for multiband image reconstruction and post-processing features (volumetry, Kurtosis, RS fMRI, RSI, and, as applicable, further advanced modules) executable on commercially available image processing workstations. *GE Research Pack II* is optimized for use with the investigational 32-channel head coil for 3.0T GE scanners (Nova Medical).

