8. DATA ANALYSIS AND STATISTICS

8.1. Overview

This exploratory hypothesis-generating study is primarily conducted to collect data for subsequent engineering and scientific analyses outside of this study. The report will summarize the subjects enrolled and type of datasets collected. Exploratory data analyses will not be part of the report unless deemed necessary. General statistical methods described in this section and/or other parametric or non-parametric methods, as appropriate for data analysis depending

on the distribution of collected data, will be applied in exploratory analysis. Based on actual data distribution from this exploratory study, data transformation may be performed for data analysis.

Clinical Neuropsychological Assessment will not be part of this study report either, but will be included in the exploratory analysis. Before statistical analysis, outcomes from a particular Clinical Neuropsychological Assessment may be summarized in a clinically meaningful way, such as totaling the score of all or some items in the assessment, determining an overall score or severity, or other methods.

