8.2. Statistical Analysis Methods

8.2.1. General Statistical Method

As necessary to support exploratory analyses for scientific and engineering purposes and/or regulatory submission, continuous variables will be summarized with standard descriptive statistics including counts, means, standard deviations, medians, and minimum, maximum. Categorical variables will be summarized with frequencies and percentages.

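### Section 8.2.3 allows LOCF or interpolation in the exploratory analysis, where the neuropsychological battery is placed; LOCF to a missing mTBI Visit 4 would carry a value at least 67 days

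*Combined protocol and SAP*

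**What the plan says.** Section 8.2.3 has two sentences. The first is "No missing data imputation is planned". The second is "For subjects with missing data, outcomes may be interpolated or last observation carry forward methods may be applied in the exploratory analysis".

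Section 8.1 limits the study report to a summary of who was enrolled and which datasets were collected, and adds "Exploratory data analyses will not be part of the report unless deemed necessary". On the battery it says "Clinical Neuropsychological Assessment will not be part of this study report either, but will be included in the exploratory analysis". It also leaves room for other parametric or non-parametric methods, and for later analyses outside this study. Section 8.2.1 names the summaries to be used for exploratory work or a regulatory submission: "continuous variables will be summarized with standard descriptive statistics including counts, means, standard deviations, medians, and minimum, maximum".

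The synopsis and Table 3 (Section 6.3.1) set the mTBI visits, counted from injury, at 72 hours or less, Day 7±2, and then "Visit 3 = 14 ± 2 days, and Visit 4 = 90 ± 7 days". Nothing is scheduled between the last two. For controls the synopsis says "Controls are required to attend Visits 1 and 4, but may also attend Visit 2 and 3 when available".

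Section 5.1 expects 40% attrition. Section 6.3.2 lets a subject stay on study after missing a visit other than the first. Sections 6.3.2 and 6.5 allow data collected before withdrawal to be used.

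**The concern.** LOCF assumes that a subject's outcome does not change between the last observed visit and the filled one. In this study the longest gap in the schedule falls between Day 14 and Day 90, the period in which recovery from mTBI may still be under way. Section 1.1 itself says that symptoms and white matter injury differ according to the time since injury. A method that assumes no change therefore sits badly with the reason for having four visits.

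Interpolation cannot fill a missing last visit, but it can fill Day 7 or Day 14 between observed visits. Section 8.2.3 does not say which form is meant. The linear form assumes a constant rate of change.

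Filled values raise the count, can shift the mean and can reduce the SD of change, and these are the summaries that Section 8.2.1 lists. The product of a hypothesis-generating study is a set of leads, and filling could create a lead or hide one. Section 8.2.3 does not require filled values to be labelled. It also does not say whether an optional control visit that was not attended counts as missing.

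**Working it through.** **The plan's own figure.** Targets of 210 and 105 complete datasets with 40% attrition (Section 5.1) give 210/(1 − 0.40) = 350 and 105/(1 − 0.40) = 175. Both match the stated maxima. The plan thus allows for 350 − 210 = 140 mTBI subjects without a complete dataset.

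**Carry distance to mTBI Visit 4.** The windows in days from injury are Visit 1 = 0–3, Visit 2 = 5–9, Visit 3 = 12–16 and Visit 4 = 83–97. The shortest carry is the earliest Visit 4 minus the latest prior visit; the longest is the reverse.
- From Visit 3: 83 − 16 = 67 to 97 − 12 = 85 days.
- From Visit 2: 83 − 9 = 74 to 97 − 5 = 92 days.
- From Visit 1: 83 − 3 = 80 to 97 − 0 = 97 days.

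These hold for visits inside the windows. Section 6.3.2 treats visits outside them as deviations.

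**Linear interpolation at Day 14, with Days 7 and 90 observed.** The weight is (14 − 7)/(90 − 7) = 7/83 = 8.4% of the change. As an assumed alternative, take exponential recovery with half-life h. The share of the Day 7–90 change reached by Day 14 is then (1 − 2^(−7/h))/(1 − 2^(−83/h)):
- h = 5 days: 0.621
- h = 10 days: 0.386
- h = 20 days: 0.228

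The error per filled subject is 0.537, 0.301 or 0.144 of that change. If the change is 0.5 SD and 10–20% of subjects are filled (both assumed), the group mean is off by 0.144 × 0.5 × 0.10 = 0.007 SD to 0.537 × 0.5 × 0.20 = 0.054 SD. If change is linear, the error is zero.

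**LOCF at Day 90, illustration only.** Let p be the share of mTBI Day 90 values that are carried, and d the excess of the carried deficit over the true Day 90 deficit in those subjects. With controls unfilled, the false difference is p × d. The documents give neither p nor d. For p, suppose that all 210 complete datasets contain Day 90 and that 35, 70 or 140 other subjects are carried: 35/245 = 0.143, 70/280 = 0.25, 140/350 = 0.40. Take d = 0 to 0.5 SD.
- p = 0.143: 0 to 0.07 SD
- p = 0.25: 0 to 0.13 SD
- p = 0.40: 0 to 0.20 SD

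For rough scale, the standard error of a 210 versus 105 comparison is √(1/210 + 1/105) = 0.12 SD.

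The bias can also run the other way. If a true difference of 0.30 SD emerges only after the last observed visit, the filled analysis shows 0.30 × (1 − p) = 0.26, 0.23 or 0.18 SD.

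**Optional control visits.** Suppose a fraction f of control Day 7 values is filled by LOCF from baseline, and true change has mean zero. The SD of change is then multiplied by √(1 − f): 0.87, 0.71 or 0.50 for f = 0.25, 0.50 or 0.75. This applies only when baseline is the value carried. A control with Visit 2 but not Visit 3 has the Visit 2 change carried forward; if the SD of change is the same at both visits, the SD at Visit 3 is not reduced.

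**The case against.** The strongest reply is that no specified analysis is harmed. Filling is a permission, not a plan. The primary endpoint is the collection of data, Section 8.2.4 sets no pass/fail criteria, no contrast is named, and Section 8.1 already allows other methods. Any filled result can be rerun on the observed data. All of this stands, and it keeps the point minor. It does not make LOCF sound over 67 days or more of possible recovery.

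Five stronger readings are tempting, and the documents do not support them.
- **The two sentences of Section 8.2.3 contradict each other.** Read with Section 8.1, they can be taken as no imputation for the report and optional filling in exploratory work.
- **At most 40% of Day 90 values would be carried, so the bias is capped.** The documents never define a complete dataset as one that includes Day 90. If it does not, the share could exceed 40%. It could also be much lower: 350 is a maximum, 210 a minimum, and subjects withdrawn at the first visit may have nothing to carry.
- **The enrolment rule shows that the sponsor expects Visit 4 to be missing.** The synopsis ties control enrolment to mTBI subjects who "complete two consecutive visits and thus provide two consecutive data points (complete either Visits 1 and 2, or Visit 2 and 3"). That rule only paces control enrolment. The evidence for missing visits is the attrition estimate and Sections 6.3.2 and 6.5.
- **The battery is analysed nowhere else.** Section 8.1 also foresees analyses outside this study. The claim is limited to the analyses that this protocol describes.
- **Filling always shrinks the spread of control change.** It does so under LOCF when baseline is the value carried, but not in general. A visit marked optional may also never have been meant to count as missing.

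**Conclusion.** The concern holds as a minor, conditional one. What the documents fix is the carry distance to mTBI Visit 4 (67–85, 74–92 or 80–97 days by last visit attended) and, at nominal visit days, the 8.4% weight at Day 14 under linear interpolation. The protocol's own background argues against assuming no change over such a gap.

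The size of any bias is not fixed. It depends on the share filled, the course of recovery and the reasons for leaving, none of which the documents give. LOCF overstates a Day 90 mTBI–control difference if subjects leave before recovering, adds little or nothing if they leave after recovering, and understates a difference that appears late. The SD figures above are illustrations that leave out filling of control Day 90 values; they are not bounds. No confirmatory conclusion is at risk.

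**What to change.** Delete interpolation and LOCF from Section 8.2.3, and state that:
- longitudinal exploratory analyses of scalar outcomes use all observed visits in a likelihood-based repeated-measures model with segment, visit and segment-by-visit terms, and a suitable model for ordinal scales such as the GOS-E;
- these models assume that data are missing at random;
- optional control visits that were not attended are not filled.

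If the sponsor keeps any filling, label it and show it beside the observed-data result, with both counts.

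The cost is a wording change and a little extra analysis work. No new data are needed.

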8.2.4. Pass/Fail Criteria of the Study

There are no statistical pass/fail criteria in this hypothesis-generating study. The study will be considered successful if data collection is sufficient to meet the Sponsor's engineering and scientific goals.

9. DEVIATIONS

9.1. Management of Protocol Deviations

Deviations to the protocol may occur when necessary to protect the life or physical well-being of a subject. Except in an emergency, prior approval by the Sponsor is required for changes in, or planned deviations from this protocol. If these changes affect the scientific soundness or the safety and welfare of the subject, prior EC/IRB approval is also required. Planned Protocol Deviation documentation must be filed in the Site Study Regulatory Binder.

There are two types of unplanned protocol deviations, critical deviations and non-critical deviations. All deviations must be documented and reported, the criticality of the deviation will determine the reporting path.

Critical Deviations: Deviations that significantly affect the safety, efficacy, integrity or conduct of the study. These deviations must be reported to the Sponsor no later than 5 working days from awareness of occurrence and reported to the EC/IRB per the deviation reporting policy.

If an Investigator uses a device without obtaining informed consent, the Investigator shall consider this a critical deviation and report the event to the Sponsor and the EC/IRB within 5 working days of the occurrence.

Sponsor contact for Critical Protocol Deviations:

[name], Senior Clinical Affairs Project Manager

[contact]

[contact]

Non-Critical Deviations: Protocol deviations that DO NOT significantly affect the safety, efficacy, integrity or conduct of the trial. These deviations must be documented on the Case Report Form Protocol Deviation page and will be reviewed by the study monitor.

10.COMPLAINT HANDLING AND ADVERSE EVENT REPORTING

10.1. Foreseeable Adverse Events and Device Effects

MRI does not use ionizing radiation (high-energy radiation that can potentially cause damage to DNA, such as those found in X-rays and CT scans). MRI of 8.0T or less is widely considered non-significant risk for adults and adolescents, in accordance with the limits defined in the US FDA document Criteria for Significant Risk Investigations of Magnetic Resonance Diagnostic Devices (June 20, 2014). The safety profile of 3.0T MR scanning is well characterized, and adverse events are expected to occur at frequencies equivalent or less than conventional MRI using commercially-released scanners (adverse events are expected to occur in less than 1 in 100,000 patients; $P < 10^{-5}$).²¹ Foreseeable adverse events of 3.0T MRI scanning of the head in this study may include the following:

- During any MRI scan, the use of strong magnets may cause pacemakers, artificial limbs, and other implanted medical devices that contain metal to malfunction or heat up during the exam. Subjects are screened against site MR safety standards to mitigate these risks.
- During any MRI scan, any loose metal objects may cause damage or injury if it gets pulled toward the magnet. Subjects are screened for ferrous metallic objects before entering the scan area to minimize these risks.
- Dyes from tattoos or tattooed eyeliner can cause skin or eye irritation, and subjects may be asked to remove make-up for this reason.
- Medication patches can cause a skin burn, and subjects may be asked to remove these or other attached medical devices before scanning for this reason.
- The wire leads used to monitor an electrocardiogram (ECG) trace or respiration during a scan must be placed carefully to avoid causing a skin burn, and subjects may be asked to remove these or other attached medical devices before because of this.

- Prolonged exposure to radio waves during the scan could lead to slight warming of the body. Patients will be monitored for signs of discomfort throughout scanning to mitigate these risks.
- Rapidly changing magnetic fields can, under certain conditions, cause nerves close to the skin to become stimulated. This is known as Peripheral Nerve Stimulation (PNS). Patients will be monitored for signs of discomfort throughout scanning to mitigate these risks.
- Transient hearing loss or tinnitus can be caused by acoustic noise levels in excess of 99 dB during MRI scanning. Mandatory hearing protection will be used during scanning to minimize acoustic noise levels.
- Feelings of anxiety triggered by the partially enclosed space within the scanner or noise generated during the exam. Patients will be monitored for signs of discomfort throughout scanning to mitigate these risks.

The occurrence of these risks is mitigated to levels as low as reasonably practicable (ALARP) in accordance with the 2013 ACR Guidance Document on MR Safe Practices (J. Magn. Reson. Imaging 2013;37:501–530),²¹ which includes MR safety screening and hearing protection guidelines to minimize acoustic noise levels during scanning.

Because subjects are having a neurological assessment that includes physical and cognitive tests, there are some risks to subjects completing these assessments. These include physical or mental stress, fatigue, minor to moderate injury risk associated with physical tests (such falls or abrasions during balance tests, in rare cases), and confidentiality risks due to disclosure of personal information (e.g. sociodemographics, health, and occupational status information). The risks associated with these tests are not expected to exceed those encountered during routine examinations of head injury.

10.2. Adverse Event Definitions

Adverse Event (AE): As defined by EN ISO 14155-2011: any untoward medical occurrence, unintended disease or injury, or untoward clinical signs (including abnormal laboratory findings) in subjects, users or other persons, whether or not related to the investigational medical device.

Serious Adverse Event (SAE): As defined by EN ISO 14155 – 2011: an adverse event that

- led to death;
- led to a serious deterioration in the health of the subject, that either resulted in:
 - a life-threatening illness or injury, or
 - a permanent impairment of a body structure or a body function, or
 - in-subject or prolonged hospitalization, or
 - medical or surgical intervention to prevent life-threatening illness or injury or permanent impairment to body structure or a body function;
- led to fetal distress, fetal death or a congenital abnormality or birth defect.

Anticipated: Any adverse event and/or reaction, the specificity or severity of which is consistent with the IRB approved informed consent, protocol, investigator brochure, or product labeling.

Unanticipated adverse device effect (UADE): As defined by 21 CFR §812.3: means any serious adverse effect on health or safety or any life-threatening problem or death caused by, or

associated with, a device, if that effect, problem, or death was not previously identified in nature, severity, or degree of incidence in the investigational plan or application (including a supplementary plan or application), or any other unanticipated serious problem associated with a device that relates to the rights, safety, or welfare of subjects.

10.3. Management of Adverse Event Reporting

Any adverse events will be recorded in the subjects study record and the Adverse Event Case Report Form. Subjects will be followed for adverse events and device effects from the time they arrive for each study visit (immediately after providing informed consent for the first visit, and upon arriving to the study area for each subsequent visit, until the subject leaves the study area after each visit). The following information should be obtained:

- Description of Event
- Date of onset and resolution
- Intensity (mild, moderate, severe)
 - **Mild:** Symptom(s) barely noticeable to the subject or does not make the subject uncomfortable. The AE does not influence performance or functioning. Prescription drugs are not ordinarily needed for relief of symptom(s).
 - **Moderate:** Symptom(s) of a sufficient severity to make the subject uncomfortable. Performance of daily activities is influenced. Treatment of symptom(s) may be needed.
 - **Severe:** Symptom(s) of a sufficient severity to cause the subject severe discomfort. Treatment for symptom(s) may be given.
- Serious (yes/no)
- Relationship to device (unrelated, possibly related, probably related)
 - **Unrelated:** The adverse event is reasonably expected to be related to (or caused by) a concurrent illness, effect of another device/drug or other cause, and is unlikely related to the investigational product
 - **Possibly related:** The adverse event is reasonably expected to be related to the investigational product, and an alternative etiology is equally or less likely compared to the potential relationship to investigational product
 - **Probably related:** There is a strong relationship to investigational product, or recurs on re-challenge, and another etiology is unlikely, or there is no other reasonable medical explanation for the event.
- Treatment given and/or action taken (procedure stopped, withdrawn from study, no action)
- Anticipated (yes/no)

Adverse events will be reported to the local EC/IRB per their policy.

